2.0 STUDY OBJECTIVES

The objective of the currently proposed study is to provide pilot data for this longer-term research program. In preparation for this K23 application, we must achieve the following aims.

Aim 1: Determine the cross-sectional prevalence of undiagnosed and uncontrolled hypertension within the Cedars-Sinai Health System, as well as the patient, physician, and clinic characteristics associated with these outcomes. This will document the presence and extent of problems at this institution and reveal which populations and settings are most affected, providing insights that can be used to develop and implement future interventions.

Aim 2: Develop and pilot test new time-to-care and time-to-control measures. These measures will evaluate (1) how long it takes from when evidence exists in the EMR that patients meet criteria for hypertension before clinicians document a diagnosis and initiate treatment, (2) how long evidence exists that control is suboptimal before clinicians intensify treatment, and (3) how long each of these conditions exists before goal blood pressures are achieved. We plan to use these new measures in our future work because we expect them to be more responsive to changes in care than cross-sectional measures of control would be, and because they include both care processes (i.e., did clinicians do the right things) and outcomes (i.e., were clinical goals achieved), making it possible to distinguish whether suboptimal control is due lack of recognition, lack of action (e.g., clinical inertia), or insufficient action (e.g., suboptimal adjustment of antihypertensive medications).

Aims 3A and 3B: Aim 3A – Assess the validity, responsiveness, and potential utility of the new time-to-care and time-to-control measures. To assess validity, we can examine whether performance on the new measures is associated with performance on cross-sectional measures of blood pressure control. To assess responsiveness and potential utility, we can examine how performance changes with clinical practice. For example, the introduction of the 2017 ACC/AHA guidelines represented a marked change in the standard of care for hypertension in terms of criteria for diagnosis and blood pressure goals. If the

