prevalence of undiagnosed and uncontrolled hypertension at Cedars-Sinai is high, slow uptake of these new standards may be one explanation. However, another potential explanation is the much greater level of effort needed to attain the lower blood pressure goals. If clinicians are recognizing uncontrolled hypertension and initiating or intensifying treatment, we would expect the time-to-care measures to exhibit stable performance after 2017 while performance on the time-to-control measures and cross-sectional control rates would decline.

We will also examine how performance on the time-to-care and time-to-control measures varies based on the setting in which blood pressure is measured. If we find that that performance on these time-to-care and time-to-control measures as well as control rates are better in Primary Care, Internal Medicine, Nephrology, or Cardiology clinics than in other specialty and subspecialty clinics, this would suggest the EMR may be a useful for the screening and detection of patient populations that would benefit from efforts to make a diagnosis and initiate or intensify treatment.

Aim 3B – We will perform a pilot study of the new time-to-control measure’s responsiveness to more intensive blood pressure monitoring and intervention. This pilot will provide a subset of uncontrolled hypertensive patients with home blood pressure monitors linked to the EMR at Cedars-Sinai. This information will be monitored and acted upon weekly, allowing for a more rapid titration of medical therapy. A decrease in the time-to-control measure of blood pressure management would be a preliminary finding consistent with measure responsiveness.

Aims 4A and 4B: Aim 4A – We will conduct interview discussions to explore feasibility and acceptability of text message reminder and incentives for blood pressure medication adherence. These interview discussions will involve both patients and providers and will allow for a better understanding of existing routine behaviors that support pill-taking, appropriate messaging for text message reminders, and how to best implement the intervention.

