4.0 STUDY DESIGN AND METHODS

Achieving these objectives and aims will involve an analysis of existing data from ambulatory care visits at clinics affiliated with Cedars-Sinai Medical Center from January 1, 2014 through March 30, 2019. Via a detailed study protocol, we will establish patient eligibility criteria, specify study variables and measures for extraction from the EMR, and specify descriptive and multivariate regression analyses

related to Aims 1-3. An Advisory Board consisting of local and national experts in EMR systems, population health, hypertension, and the implementation of quality improvement interventions will provide guidance and feedback on the protocol and after we have obtained preliminary data.

Patients will need to have at least two years of data available in CS-Link to be included in the study (defined as two or more clinic visits at least two years apart and occurring within the study dates). We will include ambulatory care visits with faculty, medical delivery network, and private physicians in all specialties if they use CS-Link. We will exclude care in the emergency department, urgent care, and hospital settings because blood pressure may be temporarily elevated due to acute illness. For eligible visits, we will obtain the recorded blood pressure values, whether the blood pressure was assessed manually or automatically (if available), and the physician identity (coded).

We will define blood pressure control based on the 2017 ACC/AHA guidelines (blood pressure <130/80). In sensitivity analyses, we will also consider control based on the JNC-7 guidelines (blood pressure <140/90), due to the recent change in the standard of care.

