We will create three time-to-care measures: time-to-diagnosis, for patients who qualify for new diagnoses; time-to-initiate, for the same patients; and time-to-intensify, for patients with established diagnoses. We will create two time-to-control measures, one for patients with new and one for patients with established diagnoses. The new time-to-care and time-to-control measures will be based on the 2017 ACC/AHA guidelines. We will define undiagnosed hypertension as two ambulatory blood pressures \geq 130/80 without an ICD-9/10 code for hypertension in the preceding year; uncontrolled hypertension will be defined using the same blood pressure criterion but patients will have an ICD-9/10 code for hypertension. A new diagnosis of hypertension will be defined as an ICD-9/10 code for hypertension without a prior code or antihypertensive medication use in the preceding year. We will define treatment initiation as the first prescription for an antihypertensive medication following a new diagnosis of hypertension. Treatment intensification will represent the addition of another antihypertensive medication, an increase in the dose of an existing antihypertensive medication, and a change from one antihypertensive medication to another. We will access the 2017 guidelines and other standard sources to develop a list of antihypertensive medications. Time to care will be calculated as the number of days from the last blood pressure above goal to the documentation of the diagnosis or the initiation/intensification of treatment. Time to control will be calculated as the number of days from the last blood pressure above goal to the first blood pressure at goal.

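### Protocol 4.0 starts time-to-care and time-to-control at the last high blood pressure without saying last relative to what, and only one possible meaning delivers what Aim 2 asks for

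*Protocol*

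**What the plan says.** Protocol section 2.0 sets the target. Aim 2 is to measure "how long it takes from when evidence exists in the EMR that patients meet criteria for hypertension before clinicians document a diagnosis and initiate treatment", how long evidence of poor control stands before treatment is intensified, and "how long each of these conditions exists before goal blood pressures are achieved". Each describes a period that opens when the record first shows the problem.

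Section 4.0 then defines the measures. For care: "Time to care will be calculated as the number of days from the last blood pressure above goal to the documentation of the diagnosis", or to the start or intensification of treatment. For control: "Time to control will be calculated as the number of days from the last blood pressure above goal to the first blood pressure at goal". Neither sentence says what *last* is relative to. Earlier in the same paragraph there is a two-reading criterion ("We will define undiagnosed hypertension as two ambulatory blood pressures" at or above 130/80 without a diagnosis code). Uncontrolled hypertension uses the same criterion with a code. The clocks are not tied to that criterion.

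Section 4.0 also promises more detail: "Via a detailed study protocol, we will establish patient eligibility criteria, specify study variables and measures for extraction from the EMR". Section 7.1 plans iterative refinement of the measures, described in terms of excluding readings, visit types or populations. The SAP does not define these measures.

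For Aim 3B, section 2.0 says: "A decrease in the time-to-control measure of blood pressure management would be a preliminary finding consistent with measure responsiveness". Pilot patients are asked to upload a reading daily (section 4.0), and all uploads are recorded (section 5.4, Table 3). For the retrospective population, "For eligible visits, we will obtain the recorded blood pressure values".

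**The concern.** These measures are the product of Aim 2 and the object tested in Aims 3A and 3B. If an analyst codes the start as the high reading nearest the event, the earlier delay is discarded, and that delay is what Aim 2 sets out to measure. Time-to-control would then track visit spacing. The Aim 3A comparisons (against control rates, before and after the 2017 guideline, and between clinic types) would partly compare how often patients are seen. Time-to-care could show prompt action by clinicians who had passed over several high readings. Two analysts could also code the same sentence differently and get measures that are not comparable.

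**Working it through.** **1. What each meaning gives.** The plan has no figure to reproduce, so take an assumed patient: high on days 0, 90, 180 and 270, at goal on day 360, high again on day 450, with treatment intensified on day 180. Control is below 130/80 (section 4.0), so every reading is either high or at goal.

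| Meaning of *last* | Start day | Time-to-control (360 − start) | Time-to-care (180 − start) |
|---|---|---|---|
| Second of the two qualifying readings | 90 | 270 | 90 |
| Last high reading up to the clinician's action | 180 | not applicable | 0 |
| Last high reading before the first at goal | 270 | 90 | −90 |
| Last high reading in the record | 450 | −90 | −270 |

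From the first high reading, time-to-control would be 360 days. The 0 and the −90 in the care column come from different anchors. Zero needs the last high reading up to the action. The last high reading before goal can fall after the action and give a negative time.

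**2. The consecutive-gap result is general.** If the start is the last high reading before the first at goal, any reading between them would be either a later high reading or an earlier at-goal one, and both contradict the definition. In random sequences of 12 readings (each high with assumed probability 0.5), the two were adjacent in 19,620 of 19,620 evaluable sequences. In 18,570 of these, the last high reading in the record came after the first at goal, so that anchor gives a negative time.

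**3. Size (illustrative).** Visit spacing is an assumption built from section 7.2: 500,000 / 75,000 = 6.67 visits a year, and 365.25 / 6.67 = 54.8, about 55 days. Using all 150,000 network patients gives 500,000 / 150,000 = 3.33 a year, about 110 days. With readings high until day D and at goal from D, the median time-to-control in days from the last high reading before goal is:

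| Mean gap, pattern | D = 180 | D = 365 | D = 730 |
|---|---|---|---|
| 55, regular | 55 | 55 | 55 |
| 55, gamma (CV 0.5) | 64 | 64 | 64 |
| 55, exponential | 93 | 93 | 92 |
| 110, gamma (CV 0.5) | 128 | 129 | 129 |

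From the second high reading, the gamma medians are 159/344/709 days (55-day gaps) and 148/324/688 (110-day gaps). With D uniform on 180 to 730 days, rank correlation with D is below 0.06 for the consecutive-gap clock and 0.74 to 0.97 from the second high reading.

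**4. The same check with noisy readings.** Step 3 has no measurement variation. Now assume systolic mean 140 before control and 125 after, SD 8, independent between visits. The chance that one uncontrolled reading falls below 130 is Φ((130 − 140)/8) = Φ(−1.25) = 0.106. Over 730 days at 55-day spacing there are about 730/55 ≈ 13 readings. With about 12 looks after qualifying, the chance of a false stop is 1 − 0.894^12 ≈ 0.74; the simulation gives 73%, and the median falls from 709 to 367 days. Rank correlation from the second high reading drops to about 0.3 to 0.5, against about 0 for the consecutive-gap clock.

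**5. Aim 3B, if home uploads count.** On the consecutive-gap meaning, daily readings give 1 day against a whole visit interval for comparators. Correcting the start does not remove the imbalance. With the same assumed systolic mean (140) and SD (8) and no treatment effect, the chance of at least one of 56 daily readings below 130 is 1 − 0.894^56 = 0.998 if days are independent. It is about 89% or 74% with day-to-day correlation 0.8 or 0.9. One clinic reading gives 11%. Adding diastolic below 80 (assumed mean 85, SD 7, correlation 0.6 with systolic) gives 98%, 80% or 62% against 7%. The median time from a high reading to a first systolic below 130 is 7, 18 or 30 days with daily readings. At 55-day visits, 0.894^k first falls to one half or below at k = 7, so the median is 7 × 55 = 385 days.

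**The case against.** The strongest reply is that *last* naturally means the later of the two qualifying readings: the criterion stands a few sentences earlier, and section 2.0 states the intended start. On that reading there is no conflict with Aim 2. This stands as far as it goes. A reader might infer that section 4.0 flatly contradicts Aim 2, but the documents support only an undefined start that contradicts Aim 2 on some readings. The reply does not remove the point, because nothing in the text picks the benign meaning. The promised detailed protocol and the refinement in section 7.1 do not mention the start date.

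A second objection is that re-anchoring is no cure, because a chance low reading still ends the interval. This also stands. The correlations of 0.74 to 0.97 hold only for noise-free readings. With noise the gain is from about 0 to about 0.3 to 0.5.

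Third, Aim 2 is measure development with Advisory Board input, and Aim 3B is a 10-patient feasibility pilot that claims only a preliminary finding. This lowers the priority, but an undefined start still has to be settled before extraction.

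Finally, a reader might infer that the Aim 3B comparison is certain to be an artefact. The documents do not say whether home readings enter time-to-control. That they do is inferred from the daily uploads, Table 3 and the single scheduled in-person visit. Unequal reading frequency is also a separate issue from the meaning of *last*.

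**Conclusion.** The point holds as an undefined start date that should be fixed. Under one plain reading, time-to-control is always the gap between two consecutive readings and carries almost no information about how long pressure was uncontrolled. This follows by logic. Under another, time-to-care is 0 days whenever the clinician acts at a visit with a high reading, however many were missed before. Under a third, times can be negative. Only the second qualifying reading serves Aim 2.

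The day counts are illustrative. They rest on a crude mean visit spacing (section 7.2 gives both inputs as minimum figures) and on assumed blood pressure values. The Aim 3B point is conditional on home uploads counting.

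The scope is Aims 2, 3A and 3B. A reader might extend the concern to the randomised adherence trial, but Aim 4B and the SAP use adherence and blood pressure control, not these measures.

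**What to change.** **Section 4.0.** Replace the last reading above goal with the date on which the two-reading criterion (at or above 130/80) is first met in the episode, for new and established diagnoses alike. Say when a new episode begins. Reconcile the wording with Aim 2 in section 2.0. Stop each clock at the first subsequent event it names, and censor patients who never reach it at their last visit.

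**Section 7.1.** Name a time-to-event method for these measures. Add a sensitivity analysis that requires two consecutive at-goal readings. Under the step 4 assumptions, the chance that a given pair of uncontrolled readings is low is 0.106² ≈ 0.011, against 0.106 for one.

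**Aim 3B.** State whether home readings count. Then either compare both groups on the same kind and frequency of readings, or report the pilot's home-reading time-to-control descriptively and not as evidence of responsiveness. This concerns the analysis endpoint only, not titration.

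**Cost.** New definition text and extraction code are needed; the EMR data are the same. Patients without two high readings drop out (11% in the noise-free simulation at 180 days' duration with 110-day gamma gaps). Some dependence on visit spacing remains and should be acknowledged, as should stopping on a chance low reading in the main analysis. In Aim 3B, comparators have only about 56/54.8 = 1.0 or 56/109.6 = 0.5 visits in eight weeks, so a matched comparison is close to one look per patient and discards most home readings. The descriptive option gives up the responsiveness test that the pilot was meant to provide.

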7. Steps 5-7 will be continued for a total 8 weeks (ending 9 weeks after the in-person appointment). At that time, the clinical pharmacist will remind the patient at the end of their final phone call that they will no longer be reviewing their blood pressure or titrating their medications.
8. If at any time during the study, a patient's blood pressure is considered out of range (SBP<90 and patient symptomatic; DBP<40 and patient symptomatic; SBP>190 or DBP>115, regardless of symptoms), if the patient develops symptoms consistent with either significant hypotension or hypertension, has critical lab values (Na<125 or >150, K<3.0 or >5.5) or has any other concerning clinical finding, they will be instructed to seek care at the nearest Emergency Department.

Schedule of Procedures

Activity	In-Person Visit	Week 1	Week 2	Week 3	Week 4	Week 5	Week 6	Week 7	Week 8
Medical History/Exam	X								
Phone Call to Patient		X	X	X	X	X	X	X	X
Medication Titration	†	†	†	†	†	†	†	†	†
Laboratory Testing	†	†	†	†	†	†	†	†	†
Discharge from Study									X

X = Completed

† = Completed, as clinically indicated

Specific Protocols for Aims 4A and 4B Only:

We will also conduct interview discussions and a pilot RCT study of the use of text messaging and incentives to increase blood pressure medication adherence. Interview discussions will include 20 randomly selected patients currently taking hypertension medication and 7 clinic staff who have been employed for at least 12 months. We will conduct eight 1-hour interviews with patients recruited on a regular clinic day and one interview with providers & clinic staff to inform the intervention content (total of 27 participants). Open-ended questions will be asked before more closed-ended, probing questions so as not to bias responses and allow for exploring new leads and related topics, and to generate rich narratives. Answers to such questions will indicate the areas most important to respondents—which may, or may not, conform to our expectations. Standard probes, such as verification and compare and contrast questions, will be used. Based on the standards set by the CSMC IRB, all patients will receive \$30, while the providers and clinic staff will not receive payment. Findings from the interview discussion will be used to inform the pilot study intervention in Aim 4B.

The pilot RCT study would include 60 randomly selected hypertensive patients on hypertension treatment who may receive text message reminder and/or incentives, depending on the treatment group to which they are randomly assigned. Participants will be randomly assigned to one of three treatment groups: the control group (receives care as usual plus information on importance of establishing pill-taking routines), the message group (receives daily text messages for 3 months reinforcing information on importance of establishing pill-taking routines), or the incentive group (in addition to the same daily text messages as the message group, has a chance of winning small, intermittent rewards for taking medication in accordance with established pill-taking routine). The intervention period will last for 3 months and data monitoring will occur for an additional 6 months post-intervention totaling 9 months. Participants randomized into the incentive cohort will be eligible for a drawing only if they achieve greater than 80% medication adherence. The drawing will take place once a month for the first three months of participation with a chance to receive \$0, \$25, or \$50. Outcome measures include electronically measured medication adherence, hypertension control, adherence to established pill-taking routine, and feasibility and acceptability of intervention. We hypothesize that patients in the message and incentive groups will have higher medication adherence and hypertension control compared to the control group, and that patient in the incentive group will show greater adherence to established their pill-taking routine compared to the message and control groups.

Among participants in Aim 4B, 30 (10 from each group) will be selected to provide real-time feedback on their experiences with medication and medication taking. We will seek to enroll the first 10 participants from each group. Participants will document their experiences in real-time using a secure video platform (Medallia LivingLens). Participants may decline to participate in real-time feedback and remain in study. The submitted video diaries will be used to evaluate the feasibility, acceptability, and efficacy of interventions. In-the-moment qualitative data from participants can enhance our understanding of why trials succeed or fail, but are challenging to gather. Geography, language barriers, time constraints, and participant literacy can undermine such efforts. Instant video recordings can address this: they are immediate, and also tend to be frank and comprehensive. In recording their real-time opinions, research participants are unfettered by the need to type out their experiences - a more time consuming and (for many) difficult way to record their immediate reaction to events. To address this, we will collect in-the-moment video data from participants about their daily experience with taking medication. Diaries can focus on any aspect of their experience with the trial, including success stories or reasons for failing to take medication. The video content will provide crucial data about participants' body language, emotional state, and practical aspects of their life, such as how their home environment factors into their adherence. This will help us understand why such interventions succeed or fail.

